5.1. Objectives

This project aims to modify the “ECHT” intervention for health and body care professions and

evaluate its effectiveness. It was hypothesized that the intervention group would show a larger reduction in stigmatising attitudes towards people with visible chronic skin diseases compared to the control group.

6. Study protocol

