6.4.2. Statistical analysis

The statistical analyses will be conducted with the Statistical Package for the Social Sciences (SPSS v.27.0; IBM Corp., Armonk, NY). Descriptive statistics, i.e., absolute/relative frequencies and percentages for categorical variables and minimum, maximum, median, mean and standard-deviations for continuous variables, will be obtained for the total sample and subgroups of participants (e.g., by profession). The reliability of all questionnaires will be examined before conducting inference analyses, by calculating the Cronbach’s Alpha coefficients, considering $\alpha \geq 0.70$ as acceptable and $\alpha \geq 0.80$ as optimal.¹⁴ Assumptions of normality and sphericity will be checked by means of Shapiro-Wilk and Mauchly's Test of Sphericity, respectively.

Intervention effects on the primary outcomes will be analysed by means of 2 (Group: intervention, control) x 3 (Time: t0, t1, t2) repeated-measures analyses of variance (ANOVA). Subgroup analyses will be performed to assess potential differences between the professions. Intervention effects on the primary outcomes by profession will be analysed through 2 (Group: intervention, control) x 3 (Time: t0, t1, t2) x 3 (Profession: beauty, nurses, physical therapists) repeated-measures ANOVAs. The significance level will be established at a p-value ≤ 0.05 . Bonferroni correction for multiple testing will be applied. Effect sizes will be reported as η_p^2 , with $\eta_p^2 < 0.06$ indicating a small effect, $\eta_p^2 \geq 0.06$ indicating a medium effect and $\eta_p^2 \geq 0.14$ indicating a large effect.¹⁵ Post-hoc pairwise comparison will be used to further examine significant effects.

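### Section 6.4.2 reports effects as partial eta-squared with fixed labels and follows up only significant effects, without committing to a between-arm difference or confidence interval

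*Protocol*

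**What the plan says.** The hypothesis in Protocol section 5.1 has a direction: "the intervention group would show a larger reduction in stigmatising attitudes towards people with visible chronic skin diseases compared to the control group".

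Section 6.4.2 sets the primary analysis, one ANOVA per primary outcome: "Intervention effects on the primary outcomes will be analysed by means of 2 (Group: intervention, control) x 3 (Time: t0, t1, t2) repeated-measures analyses". It then fixes three reporting rules:

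- Effect measure: "Effect sizes will be reported as" partial eta-squared.
- Labels: a value below 0.06 is read as "indicating a small effect", from 0.06 as medium and from 0.14 as large. The small band has no lower limit.
- Follow-up: "Post-hoc pairwise comparison will be used to further examine significant effects".

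Descriptive statistics, including means and standard deviations, "will be obtained for the total sample and subgroups of participants (e.g., by profession"). Profession is given as an example; study arm is not named. The section mentions no between-arm difference and no confidence interval.

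**The concern.** The trial asks whether stigmatising attitudes fall more after the intervention seminar than after the control seminar, and by how much. Partial eta-squared for the group by time interaction does not answer that. It is a share of within-person variation, so it has neither sign nor scale unit. The sign matters here because the four primary scales in section 6.3.1 run in different directions: on three a higher score is worse, while on the Reported and Intended Behaviour Scale a lower score is worse.

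Its denominator is the within-person error, which shrinks as the correlation between T0, T1 and T2 rises. The verbal label can therefore reflect how stable the questionnaire is as much as how large the reduction is. The four scales range from 4 scored items to 15, so their retest correlations may differ, and labels may not be comparable between outcomes.

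The planned pairwise comparisons follow significant effects. For a primary outcome that misses significance, the protocol commits to nothing that shows whether the arms were similar or the estimate merely imprecise.

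**Working it through.** **Inputs.** From the protocol: two arms and three time points (6.4.2); partial eta-squared 0.02, 82 participants, power 0.80, alpha 0.05, dropout up to 20% and target 120 (6.2.1). Completers at T2: 120 × 0.8 = 96. Assumed: equal arms, a common SD, and compound symmetry with retest correlation rho. The protocol gives no rho, so a range is shown.

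**The plan's own figure.** With f² = 0.02/0.98 = 0.0204 and noncentrality f² × N × 3/(1 − rho), rho = 0.5 and N = 82 give 0.0204 × 82 × 3/0.5 = 10.04 on 2 and 160 degrees of freedom. Power is 0.809; N = 80 gives 0.799. The stated 82 is reproduced at rho 0.5.

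**Dependence on rho.** Let the arms differ by 0 at T0 and by d (in SDs) at both T1 and T2. The mean difference over time is 2d/3, so the deviations are −2d/3, d/3 and d/3. The interaction component per participant is the sum of the squared half-deviations: (4/9 + 1/9 + 1/9)d²/4 = d²/6. The error component is 2(1 − rho). Hence

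eta/(1 − eta) = d²/[12(1 − rho)].

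With d = 0.5, d²/12 = 0.02083:

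| rho | d²/[12(1 − rho)] | partial eta-squared | protocol label |
|---|---|---|---|
| 0.3 | 0.0298 | 0.029 | small |
| 0.5 | 0.0417 | 0.040 | small |
| 0.7 | 0.0694 | 0.065 | medium |
| 0.8 | 0.1042 | 0.094 | medium |
| 0.9 | 0.2083 | 0.172 | large |

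Conversely, the difference needed to reach medium is the square root of 12(1 − rho) × 0.06/0.94: 0.73 SD at rho 0.3, 0.62 at 0.5, 0.48 at 0.7 and 0.28 at 0.9.

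**Time pattern.** For differences (0, 0.5, 0), an effect gone by T2, the deviations are −1/6, 1/3 and −1/6. Their squares sum to 1/6, as they do for (0, 0.5, 0.5). Both patterns give 0.040 at rho 0.5, and they agree at every other rho too.

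**No effect at all.** With 96 completers the degrees of freedom are 2 and (96 − 2) × 2 = 188. The expected sample value under the null is 2/(2 + 188) = 0.011, which falls in the small band.

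**What an interval would add.** For the difference in change from T0 at one later time point, with 48 per arm and clustering by seminar ignored, the 95% half-width is t(0.975, 94) × √[2(1 − rho)] × √(2/48). This is 1.986 × 1.000 × 0.204 = 0.405 SD at rho 0.5, and 1.986 × 0.632 × 0.204 = 0.256 SD at rho 0.8.

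**The case against.** The strongest defence is that partial eta-squared with cited cut-offs is conventional for this analysis, matches the measure used in the sample size section, and drives no decision. Inference rests on the p-value threshold, and "Bonferroni correction for multiple testing will be applied". A separate analysis plan, not shown, may add estimates. This stands as a limit on importance. It does not remove the point, because the protocol itself sets the measure, the labels and the condition for follow-up.

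Two stronger readings are tempting and are not supported.

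*That a non-significant outcome would yield only a p-value and an unsigned ratio.* The subgroup list for descriptives is open, since profession is only an example. Arm means and SDs may well be tabulated, and a reader could then form a signed difference. What can be said is that the text does not commit to this, and that such means would carry no interval for the difference.

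*That a null result would be fully compatible with the planned effect.* One could set the half-width of 0.405 SD at rho 0.5 against the difference implied by 0.02 in the formula above, √(12 × 0.5 × 0.0204) = 0.35 SD. That compares a single-time contrast with an effect defined over two times. The matching contrast, mean of T1 and T2 minus T0, has variance factor 1.5(1 − rho) and half-width 1.986 × 0.866 × 0.204 = 0.351, so the two tie. The calculation that reproduces 82 also uses another effect-size convention, in which 0.02 corresponds to √(18 × 0.0204) = 0.61 SD. An interval of ±0.405 around zero would exclude that.

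It is also fair that the larger shifts need high correlations. In the 0.5 SD example the label stays small until rho is about 0.67 and becomes large only at about 0.87, which is high for a series that includes a three-month follow-up.

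**Conclusion.** The point holds as a weakness in estimation and reporting that should be corrected. It does not affect the validity of the F test or the stated 82 participants. For the group by time term, the chosen measure is unsigned, does not distinguish a lasting effect from one lost by T2, and labels as small even the 0.011 expected under no effect. An unchanged 0.5 SD difference moves from 0.040 to 0.172, across all three labels, as rho goes from 0.5 to 0.9. The dependence on rho is algebraic; how far it would matter here is unknown, because the protocol states no retest correlation. The figures assume equal arms and compound symmetry, and the null value also assumes 96 completers.

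**What to change.** In section 6.4.2, state that for every primary outcome, whatever its p-value, the between-arm difference in change from T0 will be reported at T1 and at T2, in scale points with a 95% CI. Give the direction of benefit for each scale. Keep partial eta-squared only as a supplement for comparison with the earlier trials, and drop the small, medium and large labels for repeated-measures terms.

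The cost is wording and slightly more reporting, since the same data supply the estimates. Some effects lose a label. Scale points will not compare directly across outcomes, because the behaviour scale is a sum and the other three are item means, but each difference can be read on its own scale.

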6.5. Quality assurance

[figure not shown]
The study will be conducted following the criteria for Good Scientific Practice. CVderm was certified in accordance with DIN ISO 9001 in 2008 and was re-certified in 2013. Furthermore, CVderm follows its own standard operating procedures (SOP).

6.6. Data protection and ethics

[figure not shown]
Before implementing this study, it will be reviewed by the ethics committee of the University Medical Center Hamburg-Eppendorf (LPEK).

Participants will receive written information on the study and the opportunity to ask questions prior to giving written informed consent. The questionnaires will be pseudonymized (encrypted with a numerical code so that only the researchers involved in the project are able to allocate personal data by using a key list).

7. Timelines and Milestones

and impact analysis
Interim report and
publications
Dissemination &
Implementation
programme
Final report &
presentations

Final report

8. References

7. World Health Organization. Global report on psoriasis, 2016.
9. Sommer R, Weinberger N-A, Spreckelsen R von, et al. A Structured Intervention for Medical Students Significantly Improves Awareness of Stigmatisation in Visible Chronic Skin Diseases: A Randomised Controlled Trial. *Acta Derm Venereol* 2022; 102: adv00641.
